- m FDG-PET scans will be taken at screening. No further FDG-PET scans will be required unless they are clinically indicated. FDG-PET scans taken within 8 weeks before signing the informed consent form (ICF) may be used as the screening FDG-PET scan.
- n CT scans of the neck, chest, abdomen, and pelvis will be obtained at screening. CT scans taken within 4 weeks before signing the ICF may be used for the screening CT scan if all of the following conditions are met:
- There is no nodal or visceral involvement noted
 - There is no clinically evident lymphadenopathy or splenomegaly by physical exam at the time of screening
 - The scan meets all quality criteria as outlined in the Imaging Manual
- For patients without nodal or visceral involvement (as determined by baseline CT scans), CT scans will be performed:
- During the cycle following the first skin response, ideally corresponding to the confirmation of the skin response, and 6 cycles (a minimum of 4 months) after that confirmed skin response
 - If there is a question of new or progressive disease in the LN/viscera
- For patients with baseline nodal/visceral disease, CT scans will be performed:
- At the end of Cycles 3, 6, 9, 12, and 15 (Days 16-21 or on Day 1 of the subsequent cycle), and per the follow-up schedule until disease progression
 - If there is a question of new or progressive disease in the LN/viscera
 - At EOT if the previous CT scan was performed more than 8 weeks before EOT
- o All questionnaires should be completed on Day 1 of Cycles 1, 2, 4, 6, 8, 10, 12, 14, and 16 before any other study procedures are performed, at EOT, and during posttreatment follow-up. EQ-5D, FACT-G, and Skindex-29 questionnaires will be employed for health-related quality of life (HRQoL) assessment from the patient’s perspective. Questionnaires may be collected by phone or by mail for patients not required to return to clinic for posttreatment follow-

Brentuximab vedotin (SGN-35)
Clinical Study Protocol C25001 Amendment 5, EudraCT: 2010-024215-14

		Screening ^a	Enrollment	Cycle 1 (21-Day Cycle)			Cycle 2 (21-Day Cycle)	Cycle 3-16 (21-Day Cycle)		EOT/ET	PTFU ^b
	Cycle (C) Day (D) Visit Window	-28 to D1	Within 72 hours of first dose	C1 D1	C1 D2 & 4	C1 D3 & 5	C2 D1	Cx D1	Cx D16- 21	30 days (±2 days) after last dose	Minimum of 24 months

up.

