All randomized patients will also be followed for survival every 12 weeks for a minimum of 24 months after the EOT visit, and then every 6 months until patient withdrawal, death, or study closure. Safety will be evaluated by the incidence of treatment-emergent adverse events (TEAEs), severity and type of AEs, and by changes from baseline in the patient's vital signs, ECOG performance status, and clinical laboratory results using the safety population.

Patients with documented PR or CR at the end of Cycle 3 and at any disease assessment thereafter, may continue treatment with study drug for up to 16 cycles with brentuximab vedotin or 48 weeks with bexarotene or methotrexate; patients with stable disease may continue therapy at the discretion of the investigator. Patients with progressive disease at any time during the study will be discontinued from study treatment (Section 7.7). Patients with increasing mSWAT prior to assessment at the end of Cycle 3 will be allowed to

Brentuximab vedotin (SGN-35)**Clinical Study Protocol C25001 Amendment 5, EudraCT: 2010-024215-14**

continue therapy until the Cycle 3 assessment if, in the investigator's opinion, the findings are due to tumor flare rather than disease progression.

Disease progression will be assessed using the response criteria included in Olsen et al, 2011, and Kempf et al, 2011^(11, 41). As described in Section 7.4.16, efficacy will be assessed per IRF, using a global response score, which consists of skin evaluation (modified severity weighted assessment tool [mSWAT] assessment), nodal and visceral radiographic assessment, and detection of circulating Sézary cells.

FDG-PET scans and CT scans of the neck, chest, abdomen, and pelvis will be performed at screening. FDG-PET scans taken within 8 weeks before signing the informed consent form (ICF) may be used as the screening FDG-PET. FDG-PET scans will not be taken after screening unless clinically indicated. CT scans taken within 4 weeks before signing the ICF may be used as the screening CT scan if all of the following conditions are met:

- There is no nodal or visceral disease involvement noted
- There is no clinically evident lymphadenopathy or splenomegaly by physical exam at the time of screening
- The scan meets all quality criteria as outlined in the Imaging Manual

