7.4.17.4 Global Response Score

Global response score (GRS) is an assessment whereby each component of the TNM(B) staging (skin, nodes, viscera, and blood for MF), has been given its own definition of response. Due to the primacy of the response in the skin in CTCL, no patient with a global objective response should have less than a PR in the skin. The global response score definition is provided in [Table 7-6](#).

Response to treatment (CR, PR, SD, PD, relapse) will be monitored on a continual basis. For all treated patients, GRS will be assessed at the end of Cycles 3, 6, 9, 12, and 15 (Days 16-21 or before dosing on Day 1 of the subsequent cycle); at EOT; and then every 12 weeks for a minimum of 24 months, and then every 6 months; or until disease progression or study closure. GRS will be determined based upon the most recent disease assessments for each component (mSWAT, CT scans, Sezary cell count for MF patients). For patients without baseline nodal/visceral involvement, the schedule for obtaining CT scans will likely not correlate with the timing of GRS determinations; thus, the nodal/visceral response

Brentuximab vedotin (SGN-35)

Clinical Study Protocol C25001 Amendment 5, EudraCT: 2010-024215-14

component should be based upon the most recent CT scan findings prior to the GRS assessment time point. Additional unscheduled GRS determinations may occur following a change in response in skin or at the time of a CT scan. Relapse will be categorized in the study endpoints definition as recurrent disease in patients with complete response.

Table 7-6 Global Response Score

Global Score	Definition	Skin	Nodes	Blood	Viscera
CR	Complete disappearance of all clinical evidence of disease	CR	All categories have CR/NI		
PR	Regression of measurable disease	CR	All categories do not have a CR/NI and no category has a PD		
		PR	No category has a PD and if any other category involved at baseline, at least one has a CR or PR		
SD	Failure to attain CR, PR or PD representative of all disease	PR	No category has a PD and if any other category involved at baseline, no CR or PR in any		
		SD	CR/NI,PR,SD in any category and no category has a PD		
PD	Progressive disease		PD in any category		
Relapse	Recurrence disease in prior CR		Relapse in any category		

Abbreviations: CR = complete response; NI = noninvolved; PR = partial response; PD = progressive disease; SD = stable disease.

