5.8.1 Primary Efficacy Endpoint

The primary endpoint of this study is ORR4 per IRF. ORR4 per IRF is defined as the proportion of patients achieving an objective response that lasts at least 4 months (i.e., duration from first response to last response is ≥ 4 months) on study as determined by an IRF. Patients whose first response occurs after the start of subsequent anti-cancer therapy but otherwise meet the primary endpoint criteria will be excluded. For objective response, a patient must achieve a CR or PR. The objective response will be considered maintained for patients with a previous CR who experience recurrent disease (i.e. Relapse) unless the criteria for progressive disease are met. Determination of objective response will be based on a GRS, which consists of skin evaluation (mSWAT assessment) by investigator, nodal and visceral radiographic assessment by IRF, and detection of circulating Sézary cells (MF only) by IRF. Skin evaluation is done at screening, before dosing on Day 1 of Cycles 1, 2, and 3, at the end of every cycle beginning at Cycle 3, EOT, and at post treatment follow-up visits. Radiographic and blood assessments are less frequent due to ethical and logistical considerations.

For patients without nodal or visceral involvement (as determined by baseline CT scans), CT scans will be performed at screening and:

- During the cycle following the first skin response, ideally corresponding to the confirmation of the skin response, and 6 cycles (a minimum or 4 months) after that confirmed skin response.
- If there is a question of new or progressive disease in the LN/viscera

For patients with baseline nodal/visceral disease, CT scans will be performed at screening and:

- At the end of Cycles 3, 6, 9, 12, and 15, and per the follow-up schedule until disease progression
- If there is a question of new or progressive disease in the LN/viscera
- At EOT if the previous CT scan was performed more than 8 weeks before EOT

A blood sample for Sézary cell enumeration in patients with MF will be collected at screening; at the end of Cycles 3, 6, 9, 12, and 15, at EOT, and per the follow-up schedule until progressive disease or study closure.

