GRS will be determined by IRF at the end of each cycle beginning at Cycle 3, EOT, and at post treatment follow-up visits until disease progression, death or study closure. The GRS assessment at each cycle will incorporate the skin response at that cycle as well as the most recent nodal, visceral, and blood responses prior to or at the time of the GRS assessment time point. CR or PR per GRS will be confirmed by sustained response in skin per mSWAT assessment at the subsequent cycle.

For patients with skin only disease at baseline, GRS is essentially determined by skin response because disease progression in node/viscera/blood is atypical in the presence of a continuing skin response. In addition, the primary endpoint is further supported by CT confirmation of continued nodal/visceral noninvolvement at the cycle after the first skin response and 6 cycles after the first confirmed skin response. For patients with baseline nodal/viscera/blood involvement, GRS assessment at each cycle will incorporate the skin response at that cycle as well as nodal, visceral, and blood responses based upon the most recent respective compartment assessments prior to the GRS assessment time point. Blood results should be within 3 cycles. The CT scans should also be within 3 cycles for patients with nodal/viscera involvement.

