blood assessments for GRS. For patients with baseline nodal/visceral/blood disease, the sensitivity analysis will only use GRS assessed at time points with concurrent nodal/viscera/blood component assessments as specified in the protocol SOE while for patients with skin-only disease, the analysis will use the same GRS assessment frequency as the primary analysis.

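### The PFS sensitivity analysis restricted to GRS with concurrent CT or blood ignores, read literally, skin progression first seen between CT visits in patients with nodal or visceral disease, and the loss can differ by arm

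*SAP*

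**What the plan says.** SAP 5.8.1 sets the GRS frequency: "GRS will be determined by IRF at the end of each cycle beginning at Cycle 3, EOT, and at post treatment follow-up visits". Each score combines that cycle's skin result with the latest available CT and blood results.

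The other compartments are assessed less often. With baseline nodal or visceral disease, on-study CT is done "At the end of Cycles 3, 6, 9, 12, and 15, and per the follow-up schedule until disease progression", and also "At EOT if the previous CT scan was performed more than 8 weeks before EOT" (Protocol Schedule of Events, footnote n; repeated in SAP 5.8.1). A further CT is triggered by a question of nodal or visceral progression. Blood in MF patients is drawn "at the end of Cycles 3, 6, 9, 12, and 15, at EOT, and per the follow-up schedule".

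Protocol Table 7-6 defines global PD as "PD in any category". Protocol 4.1 adds that "Patients with progressive disease at any time during the study will be discontinued from study treatment". Only patients without progression at EOT continue response follow-up.

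To test the carrying forward of older CT and blood results, SAP 5.8.2.1.1 adds a PFS sensitivity analysis. For patients with baseline nodal, visceral or blood disease, "the sensitivity analysis will only use GRS assessed at time points with concurrent nodal/viscera/blood component assessments as specified in the protocol SOE". For skin-only patients, "the analysis will use the same GRS assessment frequency as the primary analysis". SAP 5.8.1.1 has the same rule for ORR4. Neither section says how to date or censor a patient whose PD falls at a visit the rule leaves out.

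**The concern.** Carrying forward an old CT can hide a nodal progression or support a response call that a new scan would overturn. It cannot make a skin progression wrong, because one compartment in PD is enough. The rule nevertheless drops the whole GRS at a visit without concurrent CT, including a PD that rests on skin alone.

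For PFS that removes a documented failure. The patient stops drug and leaves response follow-up, so unless EOT supplies the event no later visit will. Censoring at the last concurrent visit is then informative, since the patient is censored because of progression.

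The arms can also differ. EOT is timed from the last dose, and brentuximab is given on Day 1 of a 21-day cycle while methotrexate is weekly and bexarotene daily. After PD at the same cycle end, EOT comes earlier on brentuximab and is less likely to fall more than 8 weeks after the last CT. PFS is a key secondary endpoint, and a robustness check that alters events by arm is hard to interpret.

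**Working it through.** **1. The plan's own figure.** SAP 5.8.2.1.2 projects about 101 PFS events from medians of 9 and 6 months, 2-year accrual and 10% dropout. Protocol 4.3 adds 10 months of follow-up. With n = 62 per arm, A = 24, F = 10, λ = ln 2/median, dropout hazard μ and L = λ + μ:

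events per arm = n·(λ/L)·[1 − (e^(−LF) − e^(−L(A+F)))/(A·L)]

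Reading 10% as cumulative over 34 months gives 47.7 + 54.3 = 102.0. Reading it as 10% per year gives 45.7 + 52.3 = 98.0. The stated 101 lies between, so these planning inputs are used below.

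**2. Does EOT bring a CT?** Take no dose delays, EOT exactly 30 days after the last dose, control dosed up to the PD visit, and CT on Day 21 of Cycle 3 (study day 63). A CT is required only if the gap exceeds 56 days.

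| Skin PD at end of | Arm | Last dose (day) | EOT (day) | Gap from CT | CT at EOT |
|---|---|---|---|---|---|
| Cycle 4 (day 84) | brentuximab | 64 | 94 | 31 | no |
| Cycle 4 | methotrexate / bexarotene | 78 / 84 | 108 / 114 | 45 / 51 | no |
| Cycle 5 (day 105) | brentuximab | 85 | 115 | 52 | no |
| Cycle 5 | methotrexate / bexarotene | 99 / 105 | 129 / 135 | 66 / 72 | yes |

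The pattern repeats at Cycles 7/8, 10/11 and 13/14; Cycle 16 behaves like Cycle 4. CT is allowed on Days 16-21. For brentuximab at Cycle 5, Day 17 (study day 59) gives 115 − 59 = 56, so no CT. Day 16 (study day 58) gives 57, so CT is done.

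**3. How many PDs are affected?** Assume exponential PD times and all PD first seen in skin at the next cycle end. Let q = e^(−21λ) with λ per day (30.4375 days per month): q = 0.948 for brentuximab and 0.923 for control. Then P(PD at Cycle 3) = 1 − q³ and P(PD at Cycle k) = q^(k−1)(1 − q) for k = 4 to 16.

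| Probability per nodal/visceral patient | Brentuximab | Control |
|---|---|---|
| On-treatment PD, 1 − q^16 | 0.573 | 0.721 |
| First visit after CT (Cycles 4, 7, 10, 13, 16) | 0.164 | 0.198 |
| Second visit after CT (Cycles 5, 8, 11, 14) | 0.134 | 0.161 |
| All PD at visits without CT | 0.298 | 0.359 |

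More PD arises at visits without CT on control, because control progresses faster. What is finally lost depends on EOT:

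- CT on Days 17-21, EOT counted only when CT is done: 0.298/0.573 = 52% of on-treatment PDs lost on brentuximab; 0.198/0.721 = 27% on control.
- CT on Day 16: 0.164/0.573 = 29% against 27%.
- EOT always counted: almost nothing lost. PD is re-dated by 94 − 84 = 10 days on brentuximab and by 24 (methotrexate) or 30 (bexarotene) days on control.
- Half of PD first seen in skin: 52% and 27% become about 26% and 14%.

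**4. Effect on the hazard ratio.** In simulations on this calendar, with lost PDs censored at the last CT visit, CT on Day 21 moves the nodal/visceral subgroup HR from about 0.66-0.70 to about 0.52-0.56, depending on the simulation set-up. With CT on Day 16 it is essentially unchanged. With equal 6-month medians and CT on Day 21 it falls from about 1.0 to about 0.8.

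**5. Whole trial.** The documents do not give the nodal/visceral share. At an assumed 20% (12.4 per arm), expected losses with CT on Days 17-21 are 12.4 × 0.298 = 3.7 on brentuximab and 12.4 × 0.198 = 2.5 on control. At 40% they are 7.4 and 4.9. These counts ignore dropout. Total events fall from about 102 to 96 (20%) or 90 (40%), and the overall HR moves from about 0.69 to about 0.66 or 0.64. With 102 events the standard error of log HR is about 2/√102 = 0.20, so the shift is ln(0.69/0.66)/0.20 = 0.2 to ln(0.69/0.64)/0.20 = 0.4 standard errors.

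**The case against.** A reader might infer that the rule always discards more progression on brentuximab and so flatters it. The documents do not support that. The rule has the same wording for both arms, and control uses the same 21-day assessment cycle (Protocol 7.4.16). The asymmetry rests on a 52-day gap against a 56-day threshold, and permitted variation can close it: a Day 16 scan gives 57 days, and one 1-week dose delay (Protocol 6.4.1) gives 59. The EOT window of ±2 days also matters, and investigators are encouraged to await independent review before stopping drug (Protocol 7.7), so the last-dose date is not fixed. This part of the objection stands, and the arm difference is conditional.

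Loss is also not the only reading. The rule refers to the protocol schedule, and Protocol 7.4.17.4 lists GRS at the ends of Cycles 3, 6, 9, 12 and 15 and at EOT. mSWAT is repeated at EOT and blood is drawn there in MF patients. If EOT counts, skin PD still present there is re-dated rather than lost. For patients with blood involvement only, that is the natural result. This also stands, but the SAP does not choose between the readings, and even this one moves a PD whose date is already documented.

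Finally, this is one of six PFS sensitivity analyses and the whole-trial shift is small. That limits the importance but does not justify leaving out a valid PD.

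**Conclusion.** The defect holds. Read literally, the analysis ignores skin PD documented at cycle ends without CT in patients with baseline nodal or visceral disease, although that PD does not depend on the CT. The event is then re-dated to EOT or informatively censored, and the SAP does not say which.

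The size is conditional. The 52% against 27% is an upper case: all PD first seen in skin, CT on Days 17-21, no dose delay, EOT at 30 days and EOT counted only with CT. With CT on Day 16, or EOT counted, the losses are about equal. The nodal/visceral share is an assumption throughout.

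Two stronger conclusions should not be drawn. The main PFS result is not affected: SAP 5.8.2.1.1 dates PD at first documentation there, and the weighted Holm alpha is untouched. Nor would agreement between the two analyses be worthless, since a shift of 0.2 to 0.4 standard errors leaves it some value. The analysis is nevertheless a poorer check than intended, because it changes events that carrying forward cannot have distorted.

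**What to change.** In SAP 5.8.2.1.1, reword the rule so that PD in any compartment counts as an event at the date first documented, whether or not the other compartments were assessed at that visit. Apply the concurrent-assessment requirement only to non-PD scores (CR, PR, SD). State whether EOT counts as a concurrent time point, including when blood is drawn but no CT is done. Report by arm the number of patients whose first PD fell at a visit without concurrent assessment.

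The reworded analysis will differ from the main one chiefly in censoring dates, which is the part of PFS that a carried-forward CT or blood result can properly affect.

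The cost is a few sentences in the SAP and a small programming change. No new data and no change to the visit schedule are needed.

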5.8.2.1.2 Key Secondary Efficacy Analysis

Because a fixed sequential testing procedure is used between the primary endpoint and the key secondary endpoints, the key secondary endpoints will be tested only if the primary endpoint is statistically significant. The weighted Holm procedure⁽¹⁾ will be used for testing the key secondary endpoints. See Section 3.2 for details of the statistical decision rules.

Stratified log-rank test statistics will be used to compare PFS between the 2 treatment arms. The hazard ratios along with the 95% CIs will be estimated using a stratified Cox regression model. The Kaplan-Meier method will be used to estimate the distribution of the time-to-event endpoints for each treatment. Median times (if estimable), along with the 2-sided 95% CIs, will be presented.

Assuming the median PFS for the brentuximab vedotin treatment group and the physician's choice treatment group (MTX or bexarotene) are 9 and 6 months, respectively, the number of PFS events is projected to be approximately 101 at the time of the planned final analysis. This is based on an approximately 2-year enrollment period, a dropout rate of 10%, and an α level of 0.01 (2-sided), as specified in Section 3.2 per the weighted Holm procedure.

Comparison of the CR rates between the 2 treatment groups will be conducted using the stratified Cochran-Mantel-Haenszel test. The 95% CI of the difference in the response rates between the 2 treatments will also be provided. No imputation will be conducted for missing data. Patients who do not have any post baseline response assessment as specified in the protocol will be counted as nonresponders.

For skin symptoms (Skindex-29), the primary analysis will be comparing the mean symptom reduction between brentuximab vedotin and the control arms. 'Symptom reduction' is defined for each patient as the maximum reduction from baseline (sum of the 7 items related to skin symptoms normalized to a 1-100 scale). The analysis of covariance (ANCOVA) model controlling for baseline covariates (treatment group, baseline score, disease diagnosis, ECOG) will be employed for the analysis. As a sensitivity analysis, comparison of the 2 treatment groups will be conducted using the linear mixed model with repeated measures at

each time point specified in the protocol SOE. The estimation of variance—covariance matrix and statistics such as Akaike information criterion (AIC) and Bayesian information criterion (BIC) will be included in evaluating the linear mixed model. The 95% CIs of the difference of the changes from baseline between the 2 treatments will also be provided.

The total score for skin symptoms (Skindex-29) will be imputed with the mean of the other items if there is no more than 1 missing item; otherwise, it will be considered invalid and excluded from the analysis.

In addition, the entire distribution of change in Skindex-29 symptom scores at the individual patient level will be presented for each arm, respectively. The patient's largest score of change from baseline will be determined first, and then a cumulative distribution function (CDF) curve will be used to display the cumulative percentage of patients experiencing that change. It is noteworthy that the higher scores in Skindex-29 indicate worse levels of symptoms; therefore, the patient's largest score of change from baseline needs to be presented in the format of "reduction in scores" (e.g., a -10 of change needs to be presented as +10 in reduction) on the X-axis. Categorical definitions of responders or minimum important difference (MID) will be determined by scrutinizing these CDF curves.

Primary analyses of key secondary endpoints will be performed based on the ITT population. Sensitivity analyses will be performed for CR using similar statistical analyses based on the Response-Evaluable population.

